NA – not applicable
OTC – Over the counter
PAL – Product Accountability Log
PP – Per Protocol
rCDI – Recurrent *Clostridium difficile* infection
REB – Research Ethics Board
SAE – serious adverse event

SAP – Statistical Analysis Plan
VRE – vancomycin-resistant *enterococci*

4. Study Synopsis

Title	A Phase 3 Open-Label Clinical Study to Evaluate the Safety and Tolerability of Rebiotix RBX2660 (microbiota suspension) in Subjects with Recurrent Clostridium difficile Infection.
Investigational Product	RBX2660 (microbiota suspension).
Indication for Use	RBX2660 is being studied for the prevention of recurrent Clostridium difficile infection (CDI) in individuals with prior recurrent CDI infection resolved following antibiotic treatment.
Study Purpose	The purpose of this study is to evaluate the safety and tolerability of RBX2660 in subjects with recurrent CDI who have had prior recurrent CDI that was resolved with antibiotic treatment.
Definition of Recurrent CDI for Study Entry	To be considered for enrollment, a subject must have medical record documentation of: 
a current diagnosis or history of recurrent CDI as determined by the treating physician,or has had at least two separate episodes of severe CDI resulting in hospitalization.
Definition of CDI Diarrhea On-Study	The definition of CDI diarrhea for use in enrolled subjects throughout the study (Baseline visit through month 6 visit) includes: 
The passage of three or more unformed/loose stools (i.e., Bristol Stool Scale type 6-7) in 24 or fewer consecutive hours for at least two consecutive days;and a positive stool test for the presence of C. difficile as determined by the central laboratory.
Objectives	
Primary Objective: To evaluate the safety and tolerability of RBX2660 in subjects with recurrent CDI.
 
Secondary Objectives:
 
To evaluate the efficacy of RBX2660 in preventing recurrent episodes of CDI through 8 weeks after treatment.To evaluate the sustained clinical response rate of RBX2660 after treatment.

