5.3.3. Phase 2 Study Protocol 2015-01 Final Study Data

Study Design

Study protocol 2015-01 was a prospective, multicenter, open-label Phase 2 study that assessed the efficacy and safety of RBX2660 as an adjunct to antibiotics for the treatment of rCDI, as compared to a historical control population of subjects treated with standard-of-care antibiotic therapy. The study population was adults (≥ 18 years old) with rCDI who had either: a) at least two recurrences after a primary episode and had completed at least two rounds of standard-of-care oral antibiotic therapy, or b) at least two episodes of severe CDI resulting in hospitalization.

The primary efficacy objective of Treatment Success for the study was measured by the recurrence-free rate of CDI diarrhea without the need for retreatment with *C. difficile* anti-infective therapy or fecal transplant through 56 days after completion of study treatment with RBX2660. One treatment consisted of 2 enemas of RBX2660 7 ± 2 days apart. Subjects were expected to participate in the study for approximately 25-27 months: 1 month enrollment; 8 weeks efficacy follow-up; and an additional 22 months for safety follow-up.

A total of 272 subjects enrolled in the study, including 110 subjects in the Historical Control arm, 13 subjects enrolled but not treated, and 149 subjects received at least one (1) enema (Safety Population, SP). In total, 217 subjects were evaluable for treatment outcome and followed for at least 56 days (day 49 – 63) after the last treatment (Evaluable Population).

Efficacy Results

The efficacy objectives of the study were analyzed using RBX2660 treated subjects (n=142) who received at least one enema and were evaluable for a treatment outcome. This arm was compared to a closely matched Historical Control arm (n=75) chosen from a retrospective chart review of subjects treated with antibiotics for rCDI who matched key eligibility criteria and had an evaluable treatment outcome. The primary endpoint,

proportion of subjects with Treatment Success, was significantly greater in the RBX2660 arm (78.9%) as compared with the Historical Control arm (30.7%; $p<0.0001$; Pearson's chi-square test, Evaluable Population).

Safety Results

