7.3.3.3. Prohibited Medications

Prohibited medications include any oral vancomycin, metronidazole, fidaxomicin, rifaximin, nitazoxanide, bezlotoxumab, or IVIG through the 8-week follow-up assessment unless newly prescribed by a treating investigator during the course of the study as a result of recurrent CDI diagnosis. Use of IVIG for treatment of a non-CDI indication is allowed. Use of non-dietary probiotics from Screening through 8 weeks after receiving the last study enema (including OTC and prescription) is also prohibited. Medication information will be collected at the Screening visit and changes in medications will be recorded throughout the study.

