7.3.4.2. Recurrent CDI On-study

1. The passage of three or more unformed/loose (i.e., Bristol Stool Scale type 6-7) stools in 24 or fewer consecutive hours for at least two consecutive days,
2. and a positive stool test for the presence of *C. difficile* as determined by the central laboratory.

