the Baseline visit (enema administration) and it will be collected and reviewed at the 1-week follow-up visit.

Subjects may receive a second RBX2660 enema if they are deemed failures following treatment per the protocol-specified treatment failure definition. This second enema is to be administered within 21 calendar days of failure determination. If a subject receives a second RBX2660 enema, the follow-up is completed via telephone assessments at 1-week, 4-week, 8-weeks, and 6-months after completing the second enema. A final analysis and report will be completed once the last subject has completed the 6-month follow-up visit for their study treatment, including 6-month follow-up after a second RBX2660 study treatment, if applicable.

3.1.1 ***Treatment Success***

Treatment success is defined as:

- The absence of CDI diarrhea through 8 weeks after completing a study treatment.

3.1.2 ***Sustained Clinical Response***

Sustained clinical response is defined as:

- Treatment success of the presenting CDI recurrence and no new CDI episodes through 6 months after completing a study treatment.

3.1.3 ***Treatment Failure***

Treatment failure (CDI recurrence) is defined as:

- The presence of CDI diarrhea within 8 weeks of administration of a study enema, which includes a positive stool test for *C. difficile* as determined by the central laboratory.

To ensure consistency across clinical sites for the determination of study failure, the central laboratory will perform the required C. DIFF QUIK CHEK COMPLETE® Test (QCC Test) rapid enzyme immunoassay test for glutamate dehydrogenase (GDH) and toxins A and B.

In the case of suspected treatment failure where there is an immediate concern for subject safety, including the potential for serious adverse events, a test may be conducted at the site or other laboratory known to the site **in addition to** sending a sample to the central laboratory for testing. In the event, the test results from the central laboratory differ from that of a local laboratory, the results from the central laboratory will be used in determination of treatment failure and eligibility to receive a second treatment with RBX2660.

3.1.4 ***Definition of Indeterminate Treatment Outcome***

If neither the protocol-specified definition for Treatment Success nor Treatment Failure is met, the treatment outcome will be considered Indeterminate.

3.1.5 ***Determination of Treatment Outcome***

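### Treatment success ignores CDI-directed therapy given without a centrally confirmed recurrence, and no planned analysis bounds the resulting upward bias

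*SAP*

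**What the plan says.** - **Success** (SAP 3.1.1; Protocol 7.3.7): "The absence of CDI diarrhea through 8 weeks after completing a study treatment".
- **CDI diarrhea** (Protocol Section 4, Study Synopsis): "The definition of CDI diarrhea for use in enrolled subjects throughout the study (Baseline visit through month 6 visit) includes" two elements. These are the qualifying loose stools on at least two consecutive days and "a positive stool test for the presence of" *C. difficile*. Protocol 7.3.4.2 repeats both, with the test read "as determined by the central laboratory". The SAP does not restate this definition.
- **Failure** (SAP 3.1.3; Protocol 7.3.6): CDI diarrhea within 8 weeks, "which includes a positive stool test for *C. difficile* as determined by the central laboratory". Where local and central results differ, the central one decides.
- **Indeterminate** (SAP 3.1.4; Protocol 7.3.2): if neither definition is met, "the treatment outcome will be considered Indeterminate".
- **CDI drugs during the 8 weeks** (Protocol 7.3.3.3 and 9.5): not permitted "unless newly prescribed by a treating investigator during the course of the study as a result of recurrent CDI diagnosis". No central positive is required for this exception.
- **Populations and missing data**: mITT and PP drop subjects who leave before the 8-week evaluation for reasons unrelated to CDI symptoms (SAP 5.3.3, 5.3.4). The ITT analysis is described as the conservative one because it scores every exit before the 8-week assessment as a failure (SAP 6.7.1.2). SAP 7.3 allows no imputation for this endpoint.
- **A contrasting definition** (Protocol 5.3.3): study 2015-01 measured "the recurrence-free rate of CDI diarrhea without the need for retreatment with" *C. difficile* anti-infectives or fecal transplant.

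**The concern.** New CDI-directed therapy for a suspected recurrence is informative about the outcome, and it can also suppress the symptoms that a confirmed recurrence would need. The success definition does not use it at all. In a single open-label arm no control group carries the same misclassification, so any error goes straight into the reported rate.

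The situation is foreseeable. The exception in Protocol 7.3.3.3 rests on an investigator's diagnosis. The recurrence visit in Protocol 10.13 is triggered by two days of symptoms, so treatment begun sooner may precede it. After the enema, Table 10-1 schedules central *C. difficile* testing only at that visit, and the text does not tie the sample to the start of antibiotics. The diary ends at the 1-week visit, so later symptom evidence comes from visits and calls.

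Sustained clinical response requires 8-week success, so it inherits whatever happens at 8 weeks.

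**Working it through.** The plan states no power, error rate or target for this endpoint, so there is no figure to reproduce. The check applies the definitions literally and then gives a scale.

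**Step 1. Classify subjects given CDI-directed therapy for suspected recurrence within 8 weeks.**

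| Followed through 8 weeks | Two-day symptoms met | Central test | Outcome by the text |
|---|---|---|---|
| Yes | Yes | Positive | Failure |
| Yes | Yes | Negative, including a sample taken after antibiotics began or a local positive | Success |
| Yes | No, treated sooner | Any | Success |
| Yes | Yes | Missing or unevaluable | Not decided: Success if no documented event counts as absence, Indeterminate if absence must be shown |
| No, and no confirmed event | Either | Any | Indeterminate |

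For a fully observed and tested subject, success and failure are exact complements. The last two rows keep Indeterminate from being empty. As a rough guide, subjects without an evaluable or adjudicated outcome in earlier studies were:

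- 2013-001: 34 - 31 = 3, and 3/34 = 8.8% (Protocol 5.3.1)
- 2015-01: 149 - 142 = 7, and 7/149 = 4.7% (Protocol 5.3.3)
- 2017-01: 267 - 262 = 5, and 5/267 = 1.9% (Protocol 5.3.4)

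**Step 2. Follow a row 2 or row 3 subject through the analyses.**

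- mITT: treatment was completed and the subject did not exit, so the subject stays as a success.
- PP: the same, unless there is an eligibility deviation.
- ITT: only exits before the 8-week assessment become failures, so the subject stays as a success.

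For Indeterminate outcomes, the SAP settles only early exits: ITT failures, or removed from mITT and PP when unrelated to CDI symptoms. It gives no rule for an untested episode in a subject who stays, or for a symptom-related exit in mITT or PP.

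**Step 3. Scale.** Inputs: N = 750, the treatment cap (SAP 3.3), and p = 0.704, the RBX2660 success rate in study 2017-01 (Protocol 5.3.4), used only for illustration.

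95% half-width = 1.96 × √(p(1 - p)/N) = 1.96 × √(0.704 × 0.296/750) = 0.0327, about 3.3 points.

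The documents do not give the share of subjects treated without a confirmed recurrence. Assuming a share x, all true recurrences now scored as successes, the corrected rate is 70.4 - x:

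| Assumed x | Subjects (750 × x) | Rate after reclassification |
|---|---|---|
| 1% | 7.5 | 69.4% |
| 2% | 15 | 68.4% |
| 5% | 37.5 | 65.4% |
| 10% | 75 | 60.4% |

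The bias would exceed the half-width once x passes about 3.3%, or 0.0327 × 750 ≈ 25 subjects.

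**The case against.** The strongest defence is that central testing is deliberate. The plan gives consistency across sites as its reason, and a treated subject with a negative central test may not have CDI. Making a prescription a failure criterion in an open-label study would bring in investigator judgement and could bias the rate downwards. This stands, and it is why the main definition should not be replaced.

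Two stronger readings are tempting, and the documents do not support them:

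- A reader might infer that anyone treated without a central positive counts as a success. That does not follow for a lost or unsent sample: with symptoms present and no result, absence is not shown, and Indeterminate fits at least as well. Local testing is permitted only alongside a required central sample (Protocol 10.13), so diagnosis on a local test alone departs from the protocol.
- A reader might infer that Indeterminate can almost never apply. It can, through early exits and untested episodes.

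Two further limits stand. The Endpoint Adjudication Committee decides the analysed outcome under a charter that is not part of these documents, so one cannot say whether it would correct these cases. The 2015-01 definition is also only one precedent: as the protocol describes them, the definitions in 2013-001 and 2014-01 have no retreatment clause.

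Finally, the failure wording could suggest that CDI diarrhea means symptoms alone, which would make symptomatic, test-negative subjects Indeterminate. The synopsis definition argues against that, but the SAP's silence leaves it open.

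**Conclusion.** The concern holds in this form: among subjects observed through 8 weeks, those treated for suspected CDI with a negative central test, or before the two-day criterion was met, are successes by the text. Those with symptoms and no central result are unclassified, and the handling of Indeterminate outcomes is incomplete. None of the mITT, ITT or PP analyses bounds the possible upward bias, so calling the ITT analysis conservative is right only for early exits.

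The size is unknown. The range of up to 1-10 points rests on an assumed share with no anchor in the documents, on every affected subject being a true recurrence, and on 750 as denominator; the mITT set may be smaller.

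A reader might conclude that the endpoint is invalid as written. The documents do not go that far. The endpoint is secondary and descriptive, the primary endpoint is safety, and no error rate or power is affected. This is a cheap improvement, not a change on which the trial depends.

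**What to change.** Keep the central-laboratory definition for the main mITT analysis, and change the SAP as follows:

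1. **SAP 3.1**: restate the protocol's two-part definition of CDI diarrhea.
2. **SAP 3.1.4**: classify a symptomatic episode with a missing or unevaluable central result as Indeterminate.
3. **SAP 6.7.1.2**: count Indeterminate outcomes as failures in the ITT analysis. State also how they enter the mITT and PP rates, and report their number. Counting all of them as mITT failures is not proposed, because that would clash with the mITT exclusion of exits unrelated to CDI symptoms.
4. **SAP 6.7.1.2**: add a sensitivity analysis, in mITT and ITT, that scores as non-success any subject given CDI-directed anti-infectives or a fecal transplant for suspected CDI through 8 weeks without meeting the failure definition. This covers both the lack of a central positive and treatment begun before the two-day criterion.
5. Carry the same classification into sustained clinical response.

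The cost is SAP wording and some programming. Concomitant medications (Table 10-1) and treatments recorded at the recurrence visit (Protocol 10.13) are already collected. Patient management and the main protocol definition are untouched. The drawback is a less favourable sensitivity rate that may over-count failures, since some central-negative subjects do not have CDI. Read together, the main and sensitivity analyses bracket the true rate as far as this source of misclassification goes.

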5 BASELINE, SAFETY AND EFFICACY EVALUATIONS

5.1 Schedule of Events

Activity	Screening (Enrollment)	Baseline / Enema Administration (≤ 21 days from Screening)	Follow-up Visits: 1- and 8-Week (± 3 days) Assessments ¹	Follow-up Phone Assessment: Week 4 (± 3 days)	Follow-up Phone Assessment: 4 and 6 months (± 14 days)	Unscheduled Possible Recurrence Visit	Second Enema Administration ¹ (≤ 21 calendar days post Tx Failure)	Second Enema Follow-up Phone Assessment: 1-, 4-, and 8-week (± 3 days), and 6 months (± 14 days)
Informed consent obtained	X							
Demographics, medical history	X							
Prescribe/continue antibiotics for CDI symptom control	X							
Physical exam	X							
Stool sent to Rebiotix by subjects for testing and archiving (optional)	X		X	X	X	X		X
Central Lab CBC w/differential testing ³	X ³	X						
Central Lab CD4 testing	X ³							
Central Lab CMP & CRP testing	X							
C. difficile testing ⁴	X ⁴					X ⁴		
Central Lab stool and blood testing		X						
Urine pregnancy testing performed at site (if applicable)	X	X					X	
Cdiff32 Questionnaire	X	X	X		X	X		
Inclusion/exclusion criteria confirmed	X	X						
24-72hr washout period confirmed		X					X ⁷	
Enema administered		X					X	
Product complaint (if applicable)		X					X	
CDI symptoms assessed		X	X	X	X	X	X	X
Vital signs assessed	X	X				X	X	
Weight	X		X	X	X			X
Subject Diary discussed/reviewed	X	X	X ⁵					
Employment status assessed	X		X ⁶		X			
Concomitant medications	X	X	X	X	X	X	X	X
Adverse events assessed		X	X	X	X	X	X	X
Solicited events assessed ²		X	X ²					

¹ Documented treatment failures may receive a second RBX2660 enema.

² Solicited events are collected in the Subject Diary from the day of the baseline enema until the day prior to the 1-week Follow-up visit. The Subject Diary is reviewed at the 1-week Follow-up visit. Solicited events that increase in severity from Screening should be assessed for a possible adverse event.

³ Exclusion criteria for absolute neutrophil count and CD4 should be assessed based on the blood samples collected at the Screening visit.

⁴ Tested at the central laboratory

⁵ Subject Diary is reviewed only at the 1-week Follow-up visit.

⁶ Collected at the 8-week follow-up visit only.

⁷ If antibiotics were administered to manage CDI recurrence.

5.2 Time Point Algorithms

5.2.1 *Relative Day*

The date of study enema administration will be considered relative day 1, and the day before study enema administration will be relative day -1. Relative days will be calculated as follows only when the full assessment date is known (i.e., partial dates will have missing relative days, unless imputation methods have been specified):

For days before first enema:

Date of Assessment – Date of first enema administration

For days on or after first enema:

Date of Assessment – Date of first enema administration +1

For the purpose of statistical analysis, the analysis visit windows will be calculated in terms of study days since the day of the study enema administration, as illustrated in the following tables:

Table 1. Analysis Windows for Clinical Visits

Visit	Scheduled Study Day	Visit Window in Protocol (Days)	Visit Window for Analysis (Days)
Screening Visit	-20 through -1	-20 through -1	-20 through -1
Baseline/1 st Enema	1	1	1
1-week Office	8	5 - 11	5 - 11
8-weeks Office	57	54 - 60	54 - 60

Table 2. Analysis Windows for Phone Assessments

Visit	Scheduled Study Day	Visit Window in Protocol (Days)	Visit Window for Analysis (Days)
4-weeks - Phone	29	26 - 32	26 - 32
4 months - Phone	121	106 – 134	106 – 134
6 months - Phone	181	166 – 194	166 – 194

Table 3. Analysis Windows for Adverse Event Reporting by Onset Interval

Onset Interval Name	Onset Interval Analysis Window	Window for Analysis (Days)
Baseline	Screening - < Baseline	≤ -1
1-week	Baseline - 1-week	1 through 8
4-week	> 1-week - 4-week	9 through 29
8-week	> 4-week - 8-week	30 through 57
0-8-week	Baseline - 8-week	1 through 57
4-month	> 8-week - 4-month	58 through 121
6-month	> 4-month - 6-month	122 through 180+
8-week-6-month	> 8-week - 6-month	58 through 180+

If a subject has more than one assessment occurring in the same visit window, the data from the visit closest to the scheduled study day will be used for analysis. If two visits have the same distance from the scheduled study day, i.e., one visit occurs -1 day from study day, and the other visit occurs +1 day from study day, the data from the visit after the scheduled study day will be used for analysis.

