7.2. General Study Design

This is an open-label, Phase 3 study to evaluate the safety and tolerability of RBX2660 in subjects with recurrent CDI.

Up to 750 subjects may be treated in this study. Consented subjects who meet all eligibility criteria are intended to be treated. Consented subjects who do not meet the eligibility criteria will be considered screen failures and will not count towards the total number of subjects treated.

Potential subjects are expected to already be taking or have just been prescribed antibiotics to control recurrent CDI symptoms at the time of enrollment (Screening visit)

per the investigator's standard of care. Patients who have already completed their prescribed course of antibiotics to treat recurrent CDI are not eligible for enrollment (Screening visit) unless they have another recurrence that is treated with antibiotics.

Once the Screening visit is complete, in order to proceed to the Baseline Enema Administration:

1. Subject must meet all the inclusion and none of the exclusion criteria
2. Antibiotics will have been administered prior to the washout period
3. CDI symptoms must be under control leading into the antibiotic washout period (**Section 7.3.1**)

Control of CDI symptoms is defined as no longer meeting the symptomatic criteria for CDI diarrhea which is the passage of three or more unformed/loose (i.e., Bristol Stool Scale type 6-7) stools in 24 or fewer consecutive hours while taking antibiotics for the two consecutive days prior to the washout period. Thus, at a minimum the Subject Diary which is started at the Screening visit must show that symptoms are under control the two days prior to the washout period in order for the subject to receive the enema administration.

Study treatment (enema administration) is to be completed as soon as possible, but no later than 21 days after the Screening visit. A minimum of 24hr to a maximum of 72hr antibiotic washout period is required prior to administration of the study treatment.

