6.3 Baseline Assessments

Baseline assessments are collected within 20 days before or on the day of study treatment administration. Summaries for age by group (< 65 and \geq 65), sex, ethnicity, and race will be provided. Baseline height, weight and employment status will also be summarized. CDI history will be summarized by total number of episodes experienced prior to treatment. Additionally, the following will be summarized for each episode of CDI: duration (days), treatment administered, hospitalization with duration (if applicable) and available *C. difficile* test results.

The following Baseline assessments will be provided in summary table and listings:

- Medical history

- CDI history
- Laboratory testing (hematology)
- Vital signs (systolic/diastolic blood pressure [mmHg], pulse rate [beats/min], respiration rate [breaths/min], temperature [°C])

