6.8 Other Endpoints Analyses

Additionally, the other analyses will be conducted on other populations or subgroups as needed.

6.8.1 *Comparison of Baseline characteristics in subjects with treatment success with one dose of RBX2660 vs. those who were unsuccessful.*

A multivariate analysis or regression analysis will be used to identify predictors (if any) for subject success with one RBX2660 dose vs. those who were unsuccessful, for example, age or number of prior CDI events.

6.8.2 *Subject fecal microbial composition at Screening, 1-week, 4-weeks, 8-weeks, 4 months, and 6 months after study treatment.*

Descriptive statistics will be used to present the changes from Screening fecal microbial composition to those at 1-week, 4-weeks, 8-weeks, 4 months, and 6 months after study treatment for those subjects treated with RBX2660.

6.8.3 *Cdiff32 scores at Screening, 1-week, 8-weeks, 4 months, and 6 months.*

Changes from Screening in the Cdiff32 scores will be summarized using descriptive statistics. Last observation carried forward (LOCF) will be used to impute missing post-Baseline data. No inferential statistics will be performed.

6.8.4 *Recurrence of CDI within 8 weeks of second RBX2660 treatment in subjects.*

Determine the treatment success rate of those subjects who received two doses of RBX2660. This success rate will be calculated at 8 weeks following the second RBX2660 enema.

6.8.5 *Concentration of vancomycin-resistant enterococci in stool samples for subjects who were carriers at Baseline.*

Lab generated values for the presence of vancomycin resistant enterococcus based on submitted stool samples at Baseline and at 1-week, 4-weeks, 8-weeks and 4 and 6 months will be assessed for all subjects to identify any trends in the clearance of vancomycin-resistant enterococci following enema treatment.

6.8.6 *Presence of *C. difficile* in stool samples at Screening, 1-week, 4-weeks, 8-weeks, 4 months, and 6 months after study treatment.*

Lab generated values for the presence of *C. difficile* based on submitted stool samples at Baseline and at 1-week, 4-weeks, 8-weeks, 4 months, and 6 months will be assessed for all subjects to identify any trends in the clearance of *C. difficile* following enema treatment.

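### Three visit-window limits in the SAP are one day out against its own day numbering, and no rule covers an assessment in no window, so LOCF could displace an observed Cdiff32 score

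*SAP*

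**What the plan says.** **Day numbering (SAP 5.2.1).** "The date of study enema administration will be considered relative day 1, and the day before study enema administration will be relative day -1". There is no day 0. Days before the enema are the plain date difference; days on or after it are "Date of Assessment – Date of first enema administration +1".

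**Windows (SAP 5.2.1, Tables 1 and 2).** "the analysis visit windows will be calculated in terms of study days since the day of the study enema administration". In every row the analysis window equals the column headed as the protocol window:

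- Screening: −20 to −1
- 1 week: scheduled day 8, window 5–11
- 4 weeks: scheduled day 29, window 26–32
- 8 weeks: scheduled day 57, window 54–60
- 4 months: scheduled day 121, window 106–134
- 6 months: scheduled day 181, window 166–194

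If several assessments fall in one window, the one nearest the scheduled day is used. Nothing is said about an assessment that falls in none.

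**Screening interval.** Protocol 7.2 requires the enema "no later than 21 days after the Screening visit"; Protocol 9.3 and 10.8 and the SAP's own sections 3.1 and 5.1 agree on 21 days. SAP 6.3 says "Baseline assessments are collected within 20 days before or on the day of study treatment administration".

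**Tolerances.** Protocol Table 10-1 allows ±3 days at weeks 1, 4 and 8 and ±14 days at months 4 and 6. Contacts outside the window are protocol deviations; no text excludes their data.

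**Missing data.** For Cdiff32, SAP 6.8.3 states: "Last observation carried forward (LOCF) will be used to impute missing post-Baseline data". SAP 7.3 allows no other imputation apart from its adverse-event adjustments.

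**The concern.** The column that claims to restate the protocol windows does not do so in three rows. A subject can meet the protocol and still have an assessment that the SAP tables place nowhere.

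Because the analysis windows are as narrow as the protocol windows, there are also long stretches of follow-up that map to no visit. For most measures the by-visit cell would then be empty. For Cdiff32 it could be filled by LOCF with an earlier score although a later one was observed. Change scores are taken from Screening, so a subject whose Screening falls on day −21 would have no in-window reference at all, and LOCF cannot repair that because it covers only post-Baseline values.

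**Working it through.** **Inputs.** Scheduled days, printed limits and day formula: SAP 5.2.1. Tolerances: Protocol Table 10-1 and 10.12. Screening interval: Protocol 7.2.

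**Step 1. Rows that reproduce.** Window = scheduled day ± tolerance.

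- Week 1: 8 ± 3 = 5–11, as printed.
- Week 4: 29 ± 3 = 26–32, as printed.
- Week 8: 57 ± 3 = 54–60, as printed.

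**Step 2. Month rows.**

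- Month 4: 121 ± 14 = 107–135; printed 106–134.
- Month 6: 181 ± 14 = 167–195; printed 166–194.

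The printed limits run from 106 − 121 = −15 to 134 − 121 = +13 days around the scheduled day, and likewise at month 6. Days 106 and 166 are admitted although 15 days early; days 135 and 195 are left out although exactly 14 days late. The printed limits equal 120 ± 14 and 180 ± 14. SAP 6.6.2.1 does label the months as Day 120 and Day 180, but beside weeks labelled 8, 29 and 57, so that list mixes two conventions. Table 3 ends the 4-month interval at day 121 and gives the 6-month limit as 180+.

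**Step 3. Screening.** Screening exactly 21 days before the enema gives a date difference of −21. Table 1 stops at −20. That figure arises only if a day 0 is counted (1 − 21 = −20) or if the Screening day is itself counted as the first of the 21 days. The SAP formula does neither. No single convention reproduces every row.

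**Step 4. Days in no window, using the printed limits.**

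- Assigned: 7 + 7 + 7 + 29 + 29 = 79 days.
- Gaps: days 2–4 (3), 12–25 (14), 33–53 (21), 61–105 (45) and 135–165 (31), a total of 114.
- 79 + 114 = 193 days (2 to 194); 114/193 = 59.1%. Days after 194 are also unassigned.
- Cdiff32 has no 4-week visit, so that window's 7 days drop out: 114 + 7 = 121 of 193 (62.7%).
- With corrected limits, 115 of the 194 days from 2 to 195 remain unassigned. Correcting the limits does not close the gaps.

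**Step 5. What LOCF could do to Cdiff32.**

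- A month-6 score on day 195 falls in no window, and the month-4 score could be carried forward in its place.
- A month-4 score on day 135 could be replaced by the week-8 score in the same way.
- A week-8 score on day 62 is a protocol deviation but an observed value; the week-1 score could be used instead.

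**The case against.** **The SAP does not say that out-of-window data are discarded.** A reader might infer that they are. That is an inference from a missing rule: the SAP is silent on such assessments, the protocol only calls them deviations, and SAP 7.1 lists all eCRF data. What stands is the absence of a rule, and with it the possibility that LOCF overrides an observed Cdiff32 score.

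**59% is a share of calendar days, not of data.** A reader might take it as the proportion of assessments lost. The documents do not support that. No routine contact after the first enema is planned in days 61–105, for example, and sites must keep contacts in window. The protocol has the month-4 and month-6 questionnaires mailed before the call, with a reminder if they are not back, so late return is foreseen. It does not say how often this happens, or whether the completion or the return date counts.

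**The error could lie in the scheduled days.** If 120 and 180 were the intended targets, the printed limits would be right and days 135 and 195 would be 15 days late. This stands as a caution. But the same rows print 121 and 181, which match the numbering of the week visits, so the tables are inconsistent on either reading. The Screening mismatch does not depend on this choice.

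**Day −21 affects few subjects.** It matters only for those treated on the last permitted day, and only if the window overrides the named Screening visit. Both points stand.

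**Narrow windows are a legitimate choice.** They are, if the SAP also says what happens outside them. Simple contiguous windows bring their own risk. Cdiff32 is also collected at unscheduled recurrence visits, so a day-50 recurrence score could pass as week 8. Relative days count from the first enema, so an open-ended month-6 window could take in data, such as weight, from the second-enema calls.

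**Conclusion.** The Screening, 4-month and 6-month limits are wrong as written, each by one day. This takes the SAP's own numbering (enema = day 1, months 4 and 6 on days 121 and 181) and the protocol's tolerances as given. Read literally, compliant assessments on days −21, 135 and 195 have no analysis visit. Few subjects are likely to fall on those exact days.

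The missing rule for the 114 unassigned days is the larger gap in the plan. Its effect depends on how many assessments fall there, which the documents do not give and which may be small. The LOCF consequence is confined to Cdiff32, an other endpoint summarised descriptively without inference. Other by-visit data would be missing from summaries, not replaced.

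A reader might infer that the main results are at risk. They are not. The primary safety endpoint counts subjects with related TEAEs, and Table 3's adverse-event intervals are contiguous. Recurrence is dated by symptom onset (SAP 6.7.1.1.1) and adjudicated (SAP 3.1.5). The correction is worth making because it is specific and nearly free.

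**What to change.** 1. **Use one day convention throughout the SAP.** With scheduled days 121 and 181, set the limits to 107–135 and 167–195 in both columns of Table 2, and align the Day 120/180 labels in 6.6.2.1 and the 180+ limits in Table 3.
2. **Set the Screening window to −21 through −1 and section 6.3 to 21 days.** This brings the analysis window into line with the interval that the protocol and SAP 3.1 and 5.1 already state; it changes no visit rule.
3. **State for Cdiff32 that an observed scheduled-visit score takes precedence over LOCF.** Either assign an out-of-window scheduled assessment to its nominal visit, or use contiguous windows built on the Cdiff32 schedule (days 8, 57, 121, 181). The midpoints are (8 + 57)/2 = 32.5, (57 + 121)/2 = 89 and (121 + 181)/2 = 151. One example is 2–32, 33–88, 89–150 and 151 onward, which gives the equidistant days 89 and 151 to the later visit.
4. **Exclude unscheduled recurrence-visit scores and data after a second enema from those windows.** Keep the strict windows as a sensitivity analysis.
5. **State how other by-visit data in no window are handled.**

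The cost is a few table edits and programming constants, with no new data. The downside is slightly looser visit timing in the by-visit summaries, which the strict-window analysis would show.
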